#### 5.4.7 Day 7 testing and procedures

- Review of electronic medical record for length of stay and in hospital mortality
- For patients still within the hospital, repeat aerodigestive and colonic tract samples for microbiome analyses (+/- 1 day)
  - Oral swab
  - Tracheal aspirate (if the patient is on mechanical ventilation)
  - Gastric aspirate (if a gastric/enteric tube remains in place)
  - Rectal swab
  - Stool sample (if available)

#### 5.4.8 Day 30 testing and procedures

- Review of electronic medical record for clinical variables including length of stay and in hospital mortality

**Table 5-1. Schedule of Procedures**

	Pre-Entry	Screen	Baseline	Study Period	12 hrs	24 hrs	Day 7	Day 30
Documentation of Sepsis	X							
Medical Review for Inclusion/Exclusion	X	X						
Informed Consent		X						
Baseline Characteristic Measurement		X	X					
Clinical Assessment			X		X	X		
Blood Glucose Measurement			X	X				
Research Infusion				X				
Research Blood Draw			X			X		
Microbiome sampling			X			X	X	
Review of Electronic Medical Record			X			X	X	X

## 6.0 EXPERIMENTAL PROCEDURES

### 6.1 Screening

The screening form will be completed by study personnel. Diagnosis of sepsis will be based on review of medical chart by criteria in 5.1.1.

### 6.2 Clinical assessment

A clinical assessment will be performed at enrollment by a study physician and subsequently by study personnel at designated time points, to include review of clinical diagnoses, physical exam findings, microbiological, clinical, and physiological and laboratory information.

### 6.3 Study procedures

#### 6.3.1 Capillary blood glucose measurement

Blood glucose will be monitored by capillary blood measurement for the 24 hour intervention period no less frequently than every six hours starting at the time of randomization in both usual care and intervention arms. Capillary blood glucose measurements in the ICU are obtained by fingerstick utilizing less than 10 microliters of blood and do not require an additional blood draw. Current sepsis guidelines recommend preventing hyperglycemia as part of best care practices but variability remains in glycemic monitoring among critically ill patients. We will ensure blood glucose is checked routinely at least every 6 hours in patients enrolled in our study. If capillary blood glucoses are already ordered as part of the medical care in the ICU, these glucose checks will be utilized for study purposes. More frequent glycemic monitoring may be utilized as part of the care dictated by the medical ICU team and will not disqualify patient from the study.

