## 1.0 SYNOPSIS

Design	The study is a prospective randomized double-blinded placebo-controlled clinical trial to test the effects of early enteral dextrose as a therapeutic agent in critically ill patients with sepsis. Primary outcomes are differences in circulating plasma levels of the pro-inflammatory cytokine IL-6 to be tested 24 hours after randomization. Secondary outcomes include differences in circulating incretin hormone levels, differences in other pro-inflammatory cytokines including IL-1 $\beta$ and TNF- $\alpha$ , changes in intestinal microbial composition and function after intervention, glycemic control and variability as assessed by capillary blood glucose measurements and exogenous insulin dosing during the intervention period, and clinical outcomes including intensive care unit (ICU) and hospital stay and in-hospital mortality.
Duration	Study participants will be randomized within 48 hours of meeting sepsis criteria, undergo a 24 hour intervention and data collection period, and will be followed for clinical outcomes.
Sample Size	72 participants (36 patients in each arm)
Population	Men and women older than 18 years of age with evidence of sepsis admitted to the intensive care unit with an existing enteral feeding tube (or with imminent plans to place one).
Regimen	Participants will be randomized to either receive early low level enteral infusion of dextrose (intervention) or enteral free water (placebo control).

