### **5.2.3 Baseline evaluation and randomization:**

If pre-entry evaluation is acceptable, the participant will be enrolled in the study and undergo baseline testing included in Section 5.4.3. At that point, the participants will be randomized to interventional and placebo control arms. Enrollment into interventional and placebo arms will be stratified at one level by the presence or absence of pre-existing self-reported diabetes mellitus utilizing separate randomization tables. The University of Pittsburgh Medical Center Investigational Drug Service (UPMC-IDS) will be responsible for randomization, blinding, and providing the study infusion at the bedside to the clinical team.

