### **5.4.4 Study period**

- Initiation of study interventions as per protocol for 24 hrs
- Hemodynamic monitoring per ICU protocol
- Capillary blood glucose approximately every 6 hours

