### 9.2 Proposed statistical analysis

Primary statistical analysis comparing levels of pro-inflammatory cytokines will be determined by t-test (or non-parametric test if indicated) by intention-to-treat analysis. Differences in secondary continuous outcome variables between intervention and control groups will be determined by t-test or non-parametric test as appropriate. Differences in dichotomous secondary outcomes (development of

hyperglycemia, in-hospital mortality, etc.) will be determined by chi-squared analysis or Fisher's exact test as appropriate.

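### Glycemic secondary outcomes have no rule on which capillary readings count, and Section 9.2 tests them without the diabetes stratum used in randomization

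*Combined protocol and SAP*

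**What the plan says.** The Synopsis lists among the secondary outcomes "glycemic control and variability as assessed by capillary blood glucose measurements and exogenous insulin dosing during the intervention period". Section 3.3 puts glucose metabolism first among the secondary objectives.

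Section 6.3.1 sets the reading frequency as "no less frequently than every six hours starting at the time of randomization in both usual care and intervention arms" (the arm called usual care there is the placebo arm elsewhere). Section 5.4.4 schedules "Capillary blood glucose approximately every 6 hours", without named times or windows. Where checks are already ordered clinically, Section 6.3.1 says "these glucose checks will be utilized for study purposes". It then allows more: "More frequent glycemic monitoring may be utilized as part of the care dictated by the medical ICU team". Section 5.4.3 separately lists a pre-intervention capillary reading.

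Section 9.2 compares binary secondary outcomes, with development of hyperglycemia as an example, by chi-squared or Fisher's exact test, and continuous ones by t-test or a non-parametric test. No stratum term appears, although Section 5.2.3 has enrollment "stratified at one level by the presence or absence of pre-existing self-reported diabetes mellitus". Section 5.2.4 blinds the treating clinicians, nurses and investigators.

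No section gives a hyperglycemia threshold, a variability metric, a per-patient summary, or a rule for unequal numbers of readings.

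**The concern.** Two summaries that the plan leaves open, whether any reading is high and the gap between a patient's highest and lowest reading, grow with the number of readings. That number has a floor and no ceiling, and it is set after randomization by clinicians who see the glucose values. If the infusion moves glucose, it can also move the number of checks. A comparison of range would then mix the effect on glucose with an effect on measurement. An unweighted mean of all readings has a related weakness: if checks cluster after high values, high periods are over-represented.

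Separately, the tests in 9.2 ignore the one factor used to stratify randomization, which is likely to predict hyperglycemia. That costs precision in a trial of 36 per arm.

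Because neither metric nor reading set is named, whether the glycemic results are robust to this would be settled only after the data are seen.

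**Working it through.** **Inputs from the documents.** A floor of one reading per 6 h over 24 h with no ceiling (5.4.4, 6.3.1); blinded clinicians (5.2.4); stratification by diabetes (5.2.3); 36 per arm (Synopsis). The plan states no figure for any glycemic outcome, so there is none to reproduce; Section 9.1 concerns IL-6 only.

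**Assumptions, for illustration only.** Mean 140 mg/dL; between-patient and within-patient SD 25 mg/dL each; correlation between readings t hours apart exp(−t/4); a reading counts as high above 180 mg/dL. Simulation of 200,000 patients. None of these values comes from the documents, and none is a clinical proposal.

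**Step 1: dependence on the number of readings.** If each of m independent readings is high with probability q, P(at least one high) = 1 − (1 − q)^m. With q = 0.10: 1 − 0.9^5 = 0.41; 1 − 0.9^12 = 0.72; 1 − 0.9^24 = 0.92. Real readings are correlated, which weakens the dependence:

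| Interval | Readings | Any >180 | Mean range (mg/dL) | Mean within-patient SD (mg/dL) |
|---|---|---|---|---|
| 6 h | 5 | 33.9% | 54.8 | 22.2 |
| 4 h | 7 | 38.0% | 61.6 | 22.0 |
| 2 h | 13 | 44.3% | 71.6 | 21.5 |
| 1 h | 25 | 49.2% | 79.1 | 21.1 |

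Incidence and range rise with frequency. Within-patient SD on evenly spaced readings hardly moves.

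**Step 2: equal glucose, one testing rule in both arms.** Suppose checks are 6-hourly, and hourly while the last reading exceeds 150 mg/dL. Each arm averages 10.6 readings, 43.4% any-high and a range of 62.6 mg/dL. The expected difference between arms is zero.

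**Step 3: same rule, mean glucose shifted in one arm, true variability unchanged.**

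| Shift (mg/dL) | Readings, triggered | Range, triggered | Range, fixed 6-hourly | Any >180, triggered | Any >180, fixed |
|---|---|---|---|---|---|
| 0 | 10.6 | 62.6 | 54.7 | 43.4% | 33.7% |
| 10 | 12.7 | 65.3 | 54.8 | 56.7% | 46.3% |
| 20 | 15.0 | 68.2 | 54.8 | 69.4% | 59.4% |

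- Range, 20 mg/dL shift: 68.2 − 62.6 = 5.6 mg/dL with triggered readings; 54.8 − 54.7 = 0.1 on the fixed set. True variability is the same, so the 5.6 is an artefact.
- Incidence: 69.4 − 43.4 = 26.0 points triggered; 59.4 − 33.7 = 25.7 points fixed. The level changes, the difference does not.
- With the trigger at 180 instead of 150, the range moves from 57.0 to 60.4 (3.4 mg/dL), and incidence equals the fixed-set value, because an extra check follows only a reading that is already high.

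The sign follows the direction of the glucose effect. Read from the bottom row up, the table describes an infusion that lowers glucose, as Section 3.1 hypothesizes: fewer checks and a spuriously narrower range.

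The fixed set above includes time 0. Dropping it lowers the level of the range, but adding a constant to every reading still leaves the range unchanged.

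**Step 4: the diabetes stratum.** Section 4.1.2 says about 40% of ICU patients develop hyperglycemia, one third of them without diabetes. If a share D of patients has diabetes (not given; assumed), the risk is 0.40 × (2/3)/D with diabetes and 0.40 × (1/3)/(1 − D) without.

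- D = 0.3: 0.267/0.3 = 89% and 0.133/0.7 = 19%.
- D = 0.4: 67% and 22%.
- D = 0.5: 53% and 27%.

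The stratum predicts the outcome strongly unless D approaches two thirds.

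**The case against.** The strongest reply is blinding. Those who decide how often to test do not know the allocation, so with equal glucose they have no reason to test one arm more. That stands, and Step 2 agrees. A reader might infer that testing frequency alone could produce a difference between arms with identical glucose. If one arm were read 6-hourly and the other hourly, 33.9% against 49.2% would have a high reading, and at 36 per arm the more-tested arm would show a significant excess 26% of the time (14% to 42% for correlation times of 8 to 2 h) against 2.5% nominal. That needs loss of blinding or chance imbalance, and the documents give no reason to expect a systematic split.

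Second, the sentence permitting extra monitoring goes on to say that it does not disqualify the patient. It concerns participation, and the preceding one can be read as letting routine checks meet the 6-hourly requirement. No section says that every extra reading enters the outcome. This also stands; the point is that nothing excludes them, and the 6-hourly floor does apply in both arms.

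Third, the plan names neither any-high incidence nor range. True, and within-patient SD on evenly spaced readings would be little affected. But leaving the metric open is itself part of the gap.

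Fourth, ignoring the stratum does not bias the comparison. Unadjusted tests after stratified randomization generally lose efficiency or are conservative. That argument is correct: the stratum point is about precision and is separate from reading frequency.

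**Conclusion.** The point holds as a gap in specification with a modest, metric-dependent consequence. If the infusion changes glucose, checks triggered by high values can create or distort a difference in range-type variability even with blinding intact: about 3 to 6 mg/dL for a 20 mg/dL shift in mean, under the assumed values and trigger rules. The between-arm difference in any-high incidence is essentially unaffected in the same scenario, at about 26 points on either reading set. No systematic difference arises when glucose is equal.

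The missing diabetes stratum is an avoidable loss of precision. Its size depends on the share of participants with diabetes, which the documents do not give.

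Only secondary outcomes are touched. The IL-6 primary analysis and its sample size are not.

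**What to change.** Change Section 9.2 only; bedside monitoring stays as it is.

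1. Analyse hyperglycemia with a Cochran-Mantel-Haenszel or exact stratified test by diabetes stratum. Analyse continuous glycemic measures with a model that includes the stratum and the baseline glucose already collected under 5.4.3.
2. Base between-arm incidence and variability on the post-baseline readings nearest 6, 12, 18 and 24 h, with stated windows. Use the time-0 reading as baseline only: it precedes the infusion, so a high value there is not development of hyperglycemia. For average glucose, use a time-weighted mean. This complements the fixed set and does not replace it, since it does nothing for incidence or variability.
3. State the hyperglycemia threshold and the variability metric before unblinding. Report the number of readings per arm. Show the all-readings analysis as a sensitivity analysis, and keep extra readings for safety.

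The cost is wording, since 6-hourly readings are already required. The downside is that short excursions between scheduled times drop out of the main comparison; the sensitivity analysis and safety data retain those that are measured.

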#### 6.3.2 Research blood draws

Blood will be drawn for plasma and serum at two time points (a) at the time of randomization and (b) after the completion of the intervention period. Approximately 10 mL of blood will be drawn each time either by venipuncture or by drawing blood from existing indwelling catheters (central venous lines or arterial lines) by the patient's bedside nurse. Blood will be drawn into several tubes including serum, EDTA, and BD P800 collection tubes.

#### 6.3.3 Microbiome sampling

Aerodigestive and colonic tract samples will be collected as follows at baseline, at the end of the infusion period, and at day 7:

**Oral swabs:** A swab will be gently rubbed on the tongue dorsum, the hard palate, the buccal mucosa, and the gingiva. Specimens will be secured in a sterile tube and stored in a locked freezer until bacterial nucleic acid extraction procedures. The procedure will be performed twice in order to obtain samples for both bacterial DNA and RNA extractions.

**Tracheal aspirates:** Five to 10 ml of tracheal aspirates will be collected using a sterile catheter during endotracheal tube suctioning if the patient remains on mechanical ventilation for the study period. Samples are collected according to standardized protocols by trained respiratory therapists. Such samples are typically collected as part of routine clinical care, but are usually discarded. Samples will be transported immediately in wet ice. Sample aliquots are stored at -80°C in a locked freezer until bacterial nucleic extraction procedures.

**Gastric aspirates:** Ten to 20 ml of gastric aspirates will be collected through the existing feeding tube. A first sample of gastric aspirate will be collected prior to initiation of experimental infusions. If no gastric aspirate obtained, then instillation of approximately 20 mL of water through the feeding tube will be performed for suctioning an adequate amount of gastric aspirate, which will be placed in a sterile specimen cup and then stored at -80°C in a locked freezer until bacterial nucleic acid extraction procedures. At 24 hr, we will obtain a gastric aspirate of 10-20 mL, again stored in similar fashion. At day 7, we will obtain a similar specimen if a feeding tube is still in place and the patient remains in the ICU.

**Stool samples:** If stool is available, a portion of the sample will be taken and stored in a sterile specimen cup, as above.

**Rectal swabs:** A swab will be gently advanced through the anal sphincter in the anal vault and gently rubbed on the rectal mucosa. Specimens will be secured in a sterile tube and stored at -80°C in a locked freezer until bacterial nucleic acid extraction procedures. The procedure will be performed twice in order to obtain samples for both bacterial DNA and RNA extractions.

## 7.0 CLINICAL MANAGEMENT ISSUES

### 7.1 Definition of adverse events

An adverse event will be defined as any unintended and unfavorable symptom or outcome during the 24 hour intervention period.

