#### **5.3.2 Study drug**

**Dextrose infusion:** 50% Dextrose solution will be infused via an oro/nasogastric tube by ICU nursing personnel per standard practices. The solution will be prepared and provided by the IDS and will be infused at a rate of 10 mL per hour for 24hr through a standard enteral nutrition pump. No additional water flushing will be necessary. Interruption/discontinuation of the infusion will be at the discretion of the treating physicians. Symptoms/signs of intolerance including vomiting or aspiration will be considered an adverse event. Gastric residuals will not be checked monitored in this study as they are not required per current critical care guidelines.

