#### 7.1.1 Vomiting

Vomiting in study and use of anti-emetic agents in participants will be recorded and incidence will be compared in intervention and placebo groups. In the event of emesis, enteral study infusion will be temporarily discontinued and will be restarted per ICU management guidelines for enteral infusions. Gastric residuals will not be monitored in this study.

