#### 7.1.3 Ischemic bowel

Ischemic bowel is a rare and potentially serious complication associated with enteral feeding occurring in less than 1% of patients. Ischemic bowel presents with intolerance to enteral feedings manifested by emesis, abdominal pain, or bloating and is characterized by ischemia or necrosis of the intestinal tissue thought to be related to diversion of blood flow to intestinal blood vessels in response to

enteral nutrients during periods of hypotension and shock. By utilizing only dextrose this risk is expected to be minimal.

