## **7.2 Reportable severe adverse events**

Critically ill septic patients represent a population in whom life-threatening multi-organ dysfunction and a high rate of untoward medical events are commonly seen routinely during their clinical course as part of their presenting medical condition. In an effort to document only clinically-relevant untoward medical events that have a greater likelihood of being study related, study endpoints (including level of glycemic control, incidence of emesis, incidence of hypotension) and certain pre-specified expected events for critically ill septic patients (see Appendix 11.3) will not be reported as serious adverse events if they occur during the 24-hour intervention period. Reportable serious adverse events (defined as fatal or immediately life-threatening or those that are permanently disabling) that are unexpected and are suspected to be related to study interventions will be disclosed within 24 hours to the IRB.

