## **7.3 Monitoring for adverse events**

Participants will be assessed for adverse events by both the study investigators and by the treating ICU team during 24 hours of study intervention. Record of adverse events in the usual care and intervention arms will be made available to the DSMB.

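### Adverse events are defined and assessed only within the 24-hour intervention period, so non-fatal enteral complications first appearing later are not systematically captured by arm

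*Combined protocol and SAP*

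**What the plan says.** Section 7.1 gives the definition: "An adverse event will be defined as any unintended and unfavorable symptom or outcome during the 24 hour intervention period". Section 7.3 sets surveillance to match: "Participants will be assessed for adverse events by both the study investigators and by the treating ICU team during 24 hours of study intervention". It then says what is done with the result: "Record of adverse events in the usual care and intervention arms will be made available to the DSMB".

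The protocol names the complications it connects with the infusion:

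- Section 5.3.2, on intolerance: "Symptoms/signs of intolerance including vomiting or aspiration will be considered an adverse event".
- Section 7.1.1: "Vomiting in study and use of anti-emetic agents in participants will be recorded and incidence will be compared in intervention and placebo groups". This is the only between-arm adverse event comparison that is spelled out.
- Section 7.1.2: DKA and hyperosmolar syndrome.
- Section 7.1.3: "Ischemic bowel is a rare and potentially serious complication associated with enteral feeding occurring in less than 1% of patients". The section adds that the risk with dextrose alone should be minimal.
- Section 7.4: severe ileus and severe abdominal pain, among the grounds for discontinuation.

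After 24 hours, Table 5-1 schedules record review at Day 7 and Day 30 and microbiome sampling at Day 7, but no clinical assessment. The Day 7 review in 5.4.7 is described as "Review of electronic medical record for length of stay and in hospital mortality". Section 5.4.8 (Day 30) refers more openly to clinical variables that include those two items, and names no toxicity.

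**The concern.** The listed complications need not be diagnosed while the 24-hour clock runs. In a full-length infusion, product given at hour 23 has one hour of adverse event observation left (24 − 23 = 1). Bowel ischemia or aspiration that begins in the period may be recognized the next day. The protocol's own reasoning also looks past hour 24: section 4.1.6 describes the stomach as a source of aspirated bacteria with later infectious consequences, and 5.4.7 resamples the airway and gut at Day 7. Biological effect is thus followed to Day 7, while toxicity is followed to hour 24.

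At stake is the completeness of the safety record. Section 4.1.4 says the approach has not been tried in humans, and 4.2.1 presents the trial as informing a larger one. The DSMB reviews trial safety every six months, and the adverse event record it is promised in 7.3 uses the restricted definition.

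**Working it through.** The plan states no figure that depends on the adverse event window, so there is none to reproduce. The check has three parts.

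**1. Follow one event through the text.** Take a non-fatal ischemic bowel or aspiration event first diagnosed at hour 30.

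| Place | Would it be counted? |
|---|---|
| 7.1 definition | No: outside the 24-hour period |
| 7.3 assessment | No: assessment covers the same 24 hours |
| Table 5-1 | Clinical assessment at baseline, 12 h and 24 h only |
| 5.4.7, Day 7 review | Names stay and in-hospital mortality only |
| 5.4.8, Day 30 review | Open-ended wording, but no toxicity named |
| 7.2, serious event reporting | Requires the event to be unexpected and suspected to be related; Appendix 11.3 lists both aspiration and ischemic bowel as expected |
| 7.7, IRB reporting | No time limit stated; its adverse event wording uses the term that 7.1 restricts, while unexpected problems are a separate, case-by-case category |

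No row produces a systematic count by arm.

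**2. What a longer window could show for a rare event.** Inputs: 36 per arm and 72 in total (Synopsis); ischemic bowel below 1% (7.1.3), with 1% used as a ceiling.

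- Expected cases in one arm: 36 × 0.01 = 0.36 at most.
- Chance of at least one case, 1 − (1 − p)^n: 1 − 0.99^36 = 30% in one arm; 1 − 0.99^72 = 52% in the whole trial. At an assumed 0.5%, these are 17% and 30%.
- One-sided 95% upper bound after zero cases, 1 − 0.05^(1/n): 8.0% for n = 36; 4.1% for n = 72.

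None of these figures depends on when follow-up stops. For rare harms, sample size is the main limit.

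**3. What a short window could cost for a commoner event.** The documents give no rates, so these are assumptions: cumulative risk to the end of a longer window of 10% on placebo and 30% (or 40%) on dextrose, with the same share f of events in both arms falling inside 24 hours. The risk seen in each arm is then f times its cumulative risk. Exact power of Fisher's test, 36 per arm, two-sided 0.05:

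| f | 10% v 30% | 10% v 40% |
|---|---|---|
| 1 | 47% | 80% |
| 0.75 | 31% | 61% |
| 0.5 | 15% | 35% |
| 0.25 | 2% | 7% |

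If f is near 1, little is lost. The documents do not say what f is, or whether it is equal in the two arms.

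**The case against.** A 24-hour window for a 24-hour exposure can be defended on attribution. After hour 24, feeding is at the ICU team's discretion in both arms (5.3.3, 7.6), so later vomiting, aspiration or ileus increasingly reflects feeding rather than study product. Appendix 11.3 lists these events as expected in sepsis. Examples at hour 25 or the next day argue for a short tail more than for six further days. This has force, although the protocol does not give that rationale. It supports reporting the later period separately, with feeding status, rather than not collecting it.

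The gap is also narrower than it may look:

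- The cut-off is the 24-hour period, not the end of infusion. If the infusion stops early (7.6), events up to hour 24 still count.
- In-hospital death and stay are reviewed at Day 7 and Day 30, so a fatal late in-hospital event is counted as a death, though not by cause.
- Emesis is listed as a clinical measure in section 5.0 without a stated window.
- Section 7.7 gives the DSMB trial safety without a time limit, and has the team review unanticipated problems monthly. A reader might infer that the DSMB could never learn of a late event; the text does not go that far.

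A reader might also infer that the safety comparison will be falsely reassuring. The documents give no late-event rate and no arm difference, so that does not follow. Nor does 24/168 = 14% measure the loss: it is a share of the hours to Day 7, not of events.

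**Conclusion.** The point holds as a gap in ascertainment. Read together, 7.1, 7.3, 5.4.7, 5.4.8 and Table 5-1 leave non-fatal enteral complications that first appear after hour 24 without systematic capture by arm. This rests on the text as written and needs no assumption about rates.

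The size and direction of any resulting error are unknown. A short window would hide a difference if dextrose-related events present late; a long one could dilute it if later events are mostly sepsis or feeding. The power figures above are illustrations under assumed risks, not estimates for this trial.

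Extending the window will not establish that a rare harm is absent: zero ischemic bowel cases in 36 patients is compatible with a true risk up to about 8%. What it secures is that any case that does occur is recorded in its arm. With at most 0.36 cases expected per arm at the 1% ceiling, a single case would carry weight.

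**What to change.** 1. In 7.1 and 7.3, extend the adverse event window beyond the intervention period, to the Day 7 record review, for the named events: vomiting, aspiration, ileus, ischemic bowel and DKA/HHS. Other events can keep the 24-hour window.
2. In 5.4.7, add these events as fields in the Day 7 review, with onset date and whether enteral feeding had started before onset. State how patients discharged or dead before Day 7 enter the denominator.
3. Report the counts by arm to the DSMB in two separate rows: within the 24-hour period, and after 24 hours to Day 7.
4. Reconcile 7.1 and 7.3 with 7.7, so that it is clear whether an event after hour 24 is an adverse event for reporting. While doing so, check 7.2: study endpoints and Appendix 11.3 events "will not be reported as serious adverse events if they occur during the 24-hour intervention period". That is a separate restriction inside the window, which this change does not remove.

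The cost is a small protocol amendment and a few extra fields in a record review that is already scheduled. The drawback is that more background sepsis and feeding-related events will be recorded; the blinded placebo arm and the split by period help to interpret them. The change affects data capture only, not treatment.
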